1.0 PRÉCIS

Background

- Small cell lung cancer (SCLC), which accounts up to 15% of all new cases of lung cancer, is a lethal cancer with a poor prognosis. About 60% of patients present with extensive-stage disease.
- The mainstay of treatment for extensive-stage SCLC (ES-SCLC) is systemic chemotherapy comprising platinum and etoposide. Despite initial sensitivity to chemotherapy, patients with ES-SCLC relapse quickly and their tumors become refractory to treatment within months. Novel systemic treatment options are needed for this highly aggressive cancer.
- Somatostatin receptors (SSTR) are expressed in neuroendocrine tumors (NETs) including SCLC. Peptide receptor radionuclide therapy (PRRT) utilizes radiolabeled SSTR2 analogs to treat NETs. $^{177}\text{Lu-DOTA}^0\text{-Tyr}^3\text{-Octreotate}$ (Lutathera) is a novel ^{177}Lu -labeled somatostatin analog. Lutathera is under investigation in a number of different NETs and has an established safety profile.
- The clinical efficacy of immune checkpoint blockade targeting the programmed death 1 (PD-1) pathway has been shown in various cancers including SCLC. Nivolumab is a fully human IgG4 monoclonal antibody that targets PD-1. Preliminary data from studies of nivolumab monotherapy or nivolumab/ipilimumab combination therapy show activity and durable responses in patients with progressive SCLC.
- Given the positive effects of radiation on immunogenic response (e.g. release of tumor antigens, induction of chemokines promoting the recruitment of T cells into the tumor, upregulation of MHC class I proteins and costimulatory molecules on tumor cells), we hypothesize that Lutathera and nivolumab will interact synergistically to provide increased therapeutic activity in patients with ES-SCLC.

Primary objectives

- The primary objective of the **phase I portion** of the study is to determine the recommended phase II dose (RP2D) of $^{177}\text{Lu-DOTA}^0\text{-Tyr}^3\text{-Octreotate}$ when given in combination with anti-PD-1 checkpoint inhibitor nivolumab in patients with small-cell lung cancer or advanced or inoperable grade I-II pulmonary NETs.
- The primary objective of the randomized **phase II portion** of the study is to compare the progression-free survival (PFS) in patients with ES-SCLC who were not progressing to first-line treatment with platinum-based therapy, after receiving combination treatment of $^{177}\text{Lu-DOTA}^0\text{-Tyr}^3\text{-Octreotate}$ and nivolumab as a maintenance therapy versus observation.

Secondary objectives

- To characterize the safety profile of $^{177}\text{Lu-DOTA}^0\text{-Tyr}^3\text{-Octreotate}$ in combination with nivolumab. [Applicable to both phase 1 and 2 portions]
- In patients who were not progressing before initiating combination therapy: [applicable to the phase 2 portion]

- To assess the disease control rate (DCR) and objective response rate (ORR) after treatment with $^{177}\text{Lu-DOTA}^0\text{-Tyr}^3\text{-Octreotate}$ plus nivolumab.
- To assess overall survival (OS).
- To assess whether the metabolic response seen on a NETSPOT[®] PET scan obtained on cycle 2 day 1 will predict response to study treatment.

Eligibility

Abbreviated Eligibility Criteria

[figure not shown]
- 1 For the phase I part, patients must have cytologically or histologically confirmed relapsed or refractory extensive-disease small-cell lung cancer (ES-SCLC) or non-progressing ES-SCLC after first line chemotherapy, or advanced or inoperable grade I-II pulmonary NETs.
- 2 For the randomized phase II part, patients must have cytologically or histologically confirmed ES-SCLC and must not have progressed after first line platinum-based chemotherapy regimen before randomization.
- 3 Toxicities of prior therapy must be resolved to grade 1 or less as per Common Terminology Criteria for Adverse Events (CTCAE) version 4.03.
- 4 Patients with tumor tissue uptake during NETSPOT[®] PET that is equal to or higher than that in normal hepatic tissue (grade ≥ 2) will be eligible. It is recommended that NETSPOT[®] PET be obtained before initiation of chemotherapy, but NETSPOT[®] PET obtained during or after completion of chemotherapy could be used for screening purpose. Only for the phase I portion, at the discretion of the principal investigator, patients with SCLC whose tumors have lower levels of uptake than liver during NETSPOT[®] PET may be eligible for the study.
- 5 Patients with a history of autoimmune disease or other diseases requiring systemic glucocorticoid or immunosuppressive therapy, previous therapy with T-cell modulating antibodies (including anti-CTLA-4, anti-PD-1, anti-PD-L1), human immunodeficiency virus (HIV) infection, or active hepatitis B or C virus infection will be excluded.
- 6 Subjects with symptomatic brain metastases will be excluded. However, subjects who have had treatment for their brain metastasis and are asymptomatic without steroid therapy for at least 2 weeks may be enrolled.
- 7 ECOG performance status of 0-1.
- 8 Adequate organ and bone marrow function (hemoglobin > 9 g/dL; absolute neutrophil count $> 1.5 \times 10^9$ /L; platelet counts $> 100 \times 10^9$ /L; serum bilirubin $< 2 \times \text{ULN}$ (except subjects with Gilbert Syndrome who must have total bilirubin < 3.0 mg/dL); alanine aminotransferase (ALT) and aspartate aminotransferase (AST) $< 2.5 \times \text{ULN}$ or $< 5 \times \text{ULN}$ if liver metastases; calculated creatinine clearance > 50 mL/min).
- 9 Life expectancy of at least 3 months.
- 10 Age > 18 years.

- 11 Ability to understand and willingness to sign a written informed consent document.
- 12 Patients who received prior anti-tumoral radionuclide therapy (with unsealed sources) are not eligible for the study.

Design

- Open-label, prospective phase I/II trial
- A randomized phase II study

Schema

CTX: chemotherapy

ES-SCLC: Extensive-stage small cell lung cancer

Pts: Patients

RP2D: Recommended phase II dose

2.0 BACKGROUND AND RATIONALE

2.1 Small cell lung cancer (SCLC)

2.1.1 Overview of SCLC

Neuroendocrine tumors (NETs) are a heterogeneous group of solid tumors that arise from neuroendocrine cells throughout the body. Neuroendocrine tumors of the lung represent a wide spectrum of disease from low-grade typical carcinoid and intermediate-grade atypical carcinoid to high-grade groups of large-cell neuroendocrine carcinoma and small-cell carcinoma (SCLC) [1]. SCLC makes up about 15% of all lung cancers and about 60% of patients with SCLC present with ES-SCLC [2]. Patients with SCLC often present with rapid onset of symptoms and significant symptoms due to rapid intrathoracic tumor growth, distant metastasis, paraneoplastic syndromes, or a combination of these features [3]. Patients with SCLC have a poor prognosis. The 5-year survival rate for limited-stage SCLC is 12%, and 1.6% for ES-SCLC [4, 5].

2.1.2 Treatment for SCLC

Treatment options for SCLC are limited. Platinum-based chemotherapy regimens have been the standard of care for a long time [6]. While the combination of platinum-based chemotherapy and thoracic radiotherapy (RT) for limited-stage SCLC produces response rates close to 90%, the duration of response is relative short, and most patients relapse after completion of treatment, although approximately 20% of patients can be cured with concomitant chemo-radiation [7, 8]. For patients with ES-SCLC, chemotherapy is the mainstay of treatment, but objective response rates (ORRs) are lower at 45-60%, with infrequent complete responses and median PFS and OS of around 5 months and 10 months, respectively [9, 10]. Second-line chemotherapy for the treatment of relapsed SCLC is less effective than the initial treatment. Topotecan is the only drug that was approved by the US Food and Drug Administration (FDA) for the treatment of relapsed SCLC in 1996 [11]. Topotecan yields objective response rates of 20-24% [12, 13]. The response rate in patients refractory to prior chemotherapy (6%) is lower than (37%) in those sensitive to first-line chemotherapy [12]. Prognosis for patients with relapsed SCLC is grim with a median overall survival of 5.4 months [12]. There is an urgent need to develop more effective therapies for patients with SCLC.

2.2 Nivolumab

Recent additions to the therapeutic armamentarium for cancer treatment are the immune checkpoint inhibitors. The programmed death-1 (PD-1)/programmed death-1 ligand (PD-L1) pathway is implicated in the mechanisms whereby tumors limit the host immune response [14]. Nivolumab is a humanized anti-PD-1 monoclonal antibody that inhibits the binding of PD-L1 to PD-1 and as a result, potentiates antitumor immune responses[15]. Emerging evidence indicates that patients whose tumors overexpress PD-L1 have improved clinical outcomes with anti-PD-L1 antibody therapy [16]. Nivolumab has been approved by the FDA in patients with melanoma, NSCLC, renal cell carcinoma, Hodgkin's lymphoma, head and neck cancer, and urothelial carcinoma[17].

2.2.1 Non-clinical studies of Nivolumab (from the Nivolumab Investigator’s Brochure, version 15, June, 2016)

[Redacted text block]

[Redacted text block]

[Redacted text block]

[Redacted text block]

[Redacted text block]

[Redacted text block]

2.2.2 Clinical studies of Nivolumab

[Redacted text block]

[Redacted text block]

[Redacted text block]

[Redacted text block]

[Redacted text block]

[Redacted text block]

[REDACTED]

2.3 ¹⁷⁷Lu-DOTA⁰-Tyr³-Octreotate

For grade 1-2 NETs of pulmonary origin, a new treatment modality is peptide receptor radionuclide therapy (PRRT) with radiolabeled somatostatin analogs [21]. In PRRT, octreotide, a somatostatin analog, is coupled with a radionuclide. Since most NETs overexpress somatostatin receptors, they are targets for radionuclide coupled to octreotide [22]. Tumors expressing somatostatin receptors can be readily visualized using radiolabeled somatostatin analogs such as [¹¹¹In-DTPA⁰]-octreotide (OctreoScan[®]; Mallinckrodt, St Louis, MO) [22] or ⁶⁸Gallium DOTATATE (NETSPOT[®]) [23]. NETSPOT[®] is a significant improvement over OctreoScan[®], with a higher sensitivity, rapid image acquisition, higher spatial resolution, higher affinity to SSTR2, less effective dose per Mbq injected, and lower radiation exposure. Several radiolabeled somatostatin analogs have been introduced with therapeutic purposes, and one of them is ¹⁷⁷Lu-DOTA⁰-Tyr³-Octreotate, a novel somatostatin analog DOTATATE, labeled with the γ (gamma) and beta particle-emitting radioisotope ¹⁷⁷Lutetium [24].

2.3.1 Non-clinical studies of Lutathera (from the Lutathera Investigator's Brochure)

[REDACTED]

[Redacted text block]

[Redacted text block]

2.3.2 Clinical studies of Lutathera (from the Lutathera Investigator’s Brochure, Version 15, June 2015)

[Redacted text block]

[Redacted text block]

[Redacted text block]

[Redacted text block]

[Redacted text block]

[Redacted text block]

[Redacted text block]

[REDACTED]

[REDACTED]

2.4 Rationale for the combination of ¹⁷⁷Lu-DOTA⁰-Tyr³-Octreotate and nivolumab

The role of combination therapy using radiotherapy and cancer immunotherapy is emerging in cancer treatment [40]. Radiation therapy can cause the release of tumor antigens and convert tumors into an *in situ* vaccine [41]. It can also induce the expression of chemokines promoting the recruitment of T cells into the tumor and increase the expression of death receptors, MHC class I proteins, and costimulatory molecules on tumor cells [41]. These responses augment antitumor effects of anti-PD-1 monoclonal antibody. Previous work also reported on radiotherapy resulting in a significant upregulation of immune effectors and cancer-testis antigens and concomitant downregulation of immune suppressors after radiotherapy in sarcomas[42]. Clinically, this synergistic effect has been observed as an abscopal effect that refers to a regression of non-irradiated lesions in patients treated with concurrent radiotherapy and immunotherapy [43]. The synergistic effects of radiation and checkpoint inhibitor therapy have also been tested in various studies as in colon cancer and glioma, where the synergistic effect of combination of anti-PD-1 or PD-L1 antibody and external beam radiation was shown with regard to tumor control and increase in PD-L1 antigen expression after radiation [44, 45]. In light of the shared features of SCLC with neuroendocrine tumors, the use of checkpoint inhibitors in SCLC, and the positive effects of radiation on immunogenic response, we believe the combination of ¹⁷⁷Lu-DOTA⁰-Tyr³-Octreotate in combination with nivolumab might lead to powerful positive interactions. Since there is no

effective maintenance therapy for patients with ES-SCLC, this population is suitable for our investigational phase I/II study. Here we propose a phase I/II study of $^{177}\text{Lu-DOTA}^0\text{-Tyr}^3\text{-Octreotate}$ and nivolumab in patients with ES-SCLC to assess the safety and efficacy of the combination. Since SSTR2 is moderately overexpressed in many tumors (e.g. breast, lymphoma, glioma, prostate, meningioma), this phase I/II trial might be pivotal to subsequently explore the combination of PRRT and checkpoint inhibitors treatment in a broader variety of tumors.

3.0 STUDY HYPOTHESIS AND OBJECTIVES

3.1 Hypothesis

We hypothesize that the combination of $^{177}\text{Lu-DOTA}^0\text{-Tyr}^3\text{-Octreotate}$ and nivolumab is safe and tolerable, and provides PFS benefit compared to observation alone in the maintenance setting in patients with ES-SCLC and no disease progression after first-line platinum-based chemotherapy.

3.2 Primary objectives

- 3.2.1** The primary objective of the phase I portion of the study is to determine the RP2D of $^{177}\text{Lu-DOTA}^0\text{-Tyr}^3\text{-Octreotate}$ when given in combination with anti-PD-1 checkpoint inhibitor nivolumab in patients with small-cell lung cancer or advanced or inoperable grade I-II pulmonary NETs.
- 3.2.2** The primary objective of the phase II portion of the study is to compare the PFS in patients with ES-SCLC who were not progressing to first-line treatment with platinum-based therapy, after receiving combination treatment of $^{177}\text{Lu-DOTA}^0\text{-Tyr}^3\text{-Octreotate}$ and nivolumab as a maintenance therapy versus observation.

3.3 Secondary objectives

- 3.3.1** To characterize the safety profile of $^{177}\text{Lu-DOTA}^0\text{-Tyr}^3\text{-Octreotate}$ in combination with nivolumab. [Applicable to both phase 1 and 2 portions]
- 3.3.2** In patients who were not progressing before initiating combo therapy: [Applicable to the phase 2 portion]
- To assess DCR and ORR after treatment with $^{177}\text{Lu-DOTA}^0\text{-Tyr}^3\text{-Octreotate}$ plus nivolumab.
 - To assess OS
 - To assess whether the metabolic response seen on a NETSPOT[®] PET scan obtained on cycle 2 day 1 will predict response to study treatment.

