7.1.1 Definitions

Evaluable for toxicity: All patients will be evaluable for toxicity from the time of their first treatment with $^{177}\text{Lu-DOTA}^0\text{-Tyr}^3\text{-Octreotate}$ and nivolumab.

Evaluable for objective response: Only those patients who have received at least one cycle of therapy, and have had their disease re-evaluated will be considered evaluable for response. These patients will have their response classified according to the definitions stated below. (Note: Patients who exhibit objective disease progression prior to the end of cycle 1 will also be considered evaluable.)

Evaluable Non-Target Disease Response: Patients who have lesions present at baseline that are evaluable but do not meet the definitions of measurable disease, have received at least one cycle of therapy, and have had their disease reevaluated will be considered evaluable for non-target disease. The response assessment is based on the presence, absence, or unequivocal progression of the lesions.

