11.2 Sample Size and Accrual

ES-SCLC (i.e. SCLC that has spread beyond the supraclavicular areas or with distant metastases) remains incurable with current management options, and patients are treated with combination chemotherapy. Several chemotherapy combinations are active in SCLC, but usually a platinum-containing regimen is chosen. The ORR of platinum-based therapy administered to patients with ES-SCLC ranges from 40 to 80%, and the median PFS ranges from 5 to 7 months in patient series treated in a clinical trial setting (phase-II/III studies) [9, 10, 48-55]. A placebo-controlled randomized phase II study of maintenance sunitinib shows that median PFS was 2.1 months in the placebo group[56].

Based on historic average clinical outcomes, we propose a clinical study that will be integrated by a dose finding approach followed by a randomized phase II study with PFS as the primary endpoint, designed to have 80% power for a two-sided 0.05 level test. The completion of the first part of the study will require approximately 8-9 months for accrual assuming 9 to 12 patients will be required for the completion of the phase I portion with the participation of 7 institutions (Georgetown Lombardi comprehensive Cancer Center, Memorial Sloan Kettering Cancer Center, University of California, Los Angeles, University of California, San Francisco, Vanderbilt University, Hackensack University Medical Center, and Walter Reed National Military Medical Center).

For the phase II portion, assuming a median PFS of 2 months following completion of first-line therapy with a platinum-based chemotherapy for ES-SCLC in the control arm, and an expected median PFS of 5 months for the maintenance therapy with $^{177}\text{Lu-DOTA}^0\text{-Tyr}^3\text{-Octreotate}$ and nivolumab in the experimental arm (hazard ratio 0.4), it will be required to document 40 PFS events from a total population of 44 patients enrolled during a period of 18 month, including a minimum follow up of 10 months, with an expected accrual rate of 3-4 patients per month and the participation of 6-7 institutions. Assuming a potential 15% dropout, the total number of patients to recruit will be 52 [57-59].

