11.3 Data Analyses Plans

PFS will be defined as the time from random assignment to disease progression or death from any cause, whichever comes first. OS will be defined as the time from random assignment to death from any cause; living patients will be censored at the date of last follow-up. Survival will be estimated and plotted by the Kaplan–Meier method. In addition, the median progression-free and overall survival times will be reported along with the 95% confidence intervals. The cox proportional hazards regression model will be used to obtain hazard ratios (HRs) and the log-rank test will be utilized to compare survival estimates between the maintenance group and the control observation group. Secondary endpoints will be analyzed when the required number of events for the primary endpoint (PFS) has been met. The DCR is defined as the proportion of patients with a best overall response of CR, PR, or SD. The ORR is defined as the proportion of patients with a best overall response of CR or PR. All randomized subjects will consist of the safety population. This population will be used for all summaries of safety data (AEs, concomitant medications, laboratory data). P-values less than 0.05 will be considered significant. All statistical analyses will be performed using SAS (Version 9.4; SAS Institute, Cary, NC). [name] will serve as the study statistician.

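### DCR and ORR are assessed only after the combination in patients who enter non-progressing; on the plan's own medians about two thirds of the expected DCR is background

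*Combined protocol and SAP*

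**What the plan says.** Objective 3.3.2, marked as applying to phase II, is "To assess DCR and ORR after treatment with" the two study drugs, in patients who were not progressing before they started them.

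Section 7.1.1 limits the response-evaluable set: "Only those patients who have received at least one cycle of therapy, and have had their disease re-evaluated will be considered evaluable for response". The one exception is progression before cycle 1 ends. Section 7.1.4.3 counts best overall response from treatment start.

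Section 11.3 states: "The DCR is defined as the proportion of patients with a best overall response of CR, PR, or SD". ORR is defined in the same way from CR and PR. Neither definition names an arm, and no estimate or test between arms is given for either rate. The log-rank and Cox comparison in 11.3 concerns survival.

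Sections 4.2.1.1, 5.1.2 and 11.1 admit to phase II only patients without progression after first-line platinum chemotherapy. Section 6.2 schedules tumor imaging every 8 weeks, within 7 days either side, in both arms.

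**The concern.** Patients selected for not progressing will often still be stable at the next scan whether or not they are treated. Stable disease counts toward DCR, so a DCR reported for the combination alone contains an untreated background of unknown size. A high value could be read as activity when much of it reflects selection at entry.

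The randomized control could measure that background, because its patients have the same imaging schedule. But an observation patient has neither a cycle of therapy nor a treatment start, so 7.1.1 and 7.1.4.3 give no way to classify that patient. Crossover does not fill the gap: it happens at progression, so those patients do not meet the non-progressing condition in 3.3.2.

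ORR has a similar but unquantified problem. Section 4.2.1.5 lets treatment start 2 weeks after the last chemotherapy dose, and 7.1.3 lets baseline measurements be up to 28 days old. A baseline scan can therefore precede the last chemotherapy dose, and later shrinkage would be credited to the combination.

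**Working it through.** **Inputs (section 11.2).** Control: "assuming a median PFS of 2 months following completion of first-line therapy"; the outside figure cited there is "median PFS was 2.1 months in the placebo group". Experimental: "an expected median PFS of 5 months for the maintenance therapy". Effect: "hazard ratio 0.4". Design: "designed to have 80% power for a two-sided 0.05 level test", with 40 events from 44 patients and 52 to recruit after 15% dropout. The scan interval and window come from 6.2.

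**Assumptions not in the documents.** Exponential PFS; 1:1 allocation (no ratio is stated); first scan 8 weeks after randomization; anyone alive and not progressed at that scan is recorded as at least SD.

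**The plan's own figures first.** The medians agree with the hazard ratio: 2/5 = 0.4. Schoenfeld events = 4 × (1.960 + 0.842)² / (ln 0.4)² = 31.4/0.840 = 37.4, so 38. The planned 40 events give about 82.6% power. 44/(1 − 0.15) = 51.8, so 52. The design reproduces to within 2 events, so its medians are a fair basis for what follows. The documents state no expected DCR or ORR.

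**Expected DCR at the first scan.** S(t) = 0.5^(t/median), with t in months (days/30.44). Eight weeks is 56/30.44 = 1.84 months.

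- Control: 0.5^(1.84/2) = 52.9%
- Combination: 0.5^(1.84/5) = 77.5%
- Difference: 24.6 points
- Background as a share of the combination DCR: 0.529/0.775 = 68%

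| Scan, from randomization | Control | Combination | Background share |
|---|---|---|---|
| 7 weeks | 57.2% | 80.0% | 72% |
| 8 weeks | 52.9% | 77.5% | 68% |
| 9 weeks | 48.8% | 75.1% | 65% |
| 10 weeks | 45.1% | 72.7% | 62% |

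The 10-week row covers a scan timed from a treatment start 2 weeks after randomization, which 4.2.1.5 allows. With a 2.1-month control median the 8-week control value is 54.5%, and the share is 0.545/0.775 = 70%.

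**Precision of a two-arm estimate.** Half-width of the 95% CI for the difference = 1.96 × √[(0.775 × 0.225 + 0.528 × 0.472)/n].

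- n = 26 per arm (all 52 recruited): 1.96 × √(0.4236/26) = 25 points
- n = 22 per arm (44 after dropout): 1.96 × √(0.4236/22) = 27 points

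Power to detect the 8-week difference is about 46% and 40% respectively; 80% power would need about 58 per arm.

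**ORR.** The documents give no rate of new CR or PR without treatment, so no parallel calculation is possible.

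**The case against.** The strongest reply is that the plan does not clearly confine these rates to one arm. Section 11.3 speaks of patients without naming an arm, 7.1.5 measures stable disease from randomization, and OS stands under the same 3.3.2 stem yet survival is compared between arms. So the objective's wording does not by itself fix the analysis set. This is right about 11.3, but it leaves the gap open: 7.1.1 and 7.1.4.3 still give no rule for an untreated patient, and a rule chosen later would be chosen with the data in view.

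Four stronger readings are tempting, and the documents do not support them.

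- A reader might infer that about half of the reported disease control is background. About half is the share of untreated patients expected to be progression-free. As a share of the combination DCR, the figure is about two thirds.
- A reader might infer that the control scans go unused. They feed the primary PFS comparison, and under the model above week-8 DCR is simply PFS at 8 weeks. What is missing is their use for these secondary endpoints.
- A reader might infer that ORR is inflated by a similar amount. No figure supports that. For patients irradiated after chemotherapy, carry-over is also less likely, since 4.2.1.5 requires at least 8 weeks between radiation and randomization.
- A reader might infer that one early scan is enough for stable disease. No minimum duration is written, but the first scheduled scan is at cycle 2 day 1 within 7 days (Appendix D), and evaluability needs a cycle, which 5.1.2 sets at 56 days. Only an unscheduled earlier scan escapes this.

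It is also fair to say that the decision impact is limited. No success rule depends on DCR or ORR, and a two-arm comparison would be imprecise. That argues for descriptive reporting, not for omitting the control.

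**Conclusion.** The point holds as a gap in the secondary analysis. As written, the plan yields a DCR for the combination that cannot be separated from the background expected in non-progressing patients, and it leaves the observation arm without a rule for DCR or ORR. Under the assumptions listed above, that background is large enough to dominate the expected result, and it remains so if the scan falls at 10 weeks (62%). The size applies to DCR only; for ORR the conclusion is qualitative. Departures from exponential PFS, such as progression clustering soon after chemotherapy ends, would move the figures. The change is worth making because the comparator data will already exist.

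**What to change.** Amend 3.3.2, 7.1.1, 7.1.4.3 and 11.3 together:

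- Classify DCR and ORR in all randomized patients of both arms, counting from randomization.
- Apply the same rule to both arms, without requiring a cycle of therapy.
- Report each rate by arm, with the difference and its 95% CI, labeled descriptive. State in advance the expected half-width for DCR of about 25 points with 26 per arm, or 27 with 22 per arm.

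The cost is wording and extra table columns from scans already in the schedule, with no new visits or patients. The DCR result will look less favorable beside its control.
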